# 6.2 Subjects enrollment and dose cohorts

The study will follow a parallel two-dose cohort and placebo design.

In the adult group, the enrollment process for subjects is as follows:

- In each planned low-dose cohort, high-dose cohort and placebo group, 72 subjects will be randomized in a 1:1:1 ratio to inject BNT162b1 or placebo vaccinated on Day 1.
- If the SRC considers that the subjects are safe with good tolerance after 14 days of observation, the boost vaccination will be conducted on Day 22.
- When the subjects in the adult group completed safety visits up to 14 days post prime vaccination, the available safety data for all subjects were summarized. If approved by the SRC,
  - o the planned dose cohort of elderly group will be initiated (see **Figure 1**). The data assessed by the SRC comprises: vital signs, TEAEs, local reactions, blood/clinical laboratory data and brief physical examination outcome.
  - o The parallel dose cohort study is conducted in the elderly group with consistent methods as those in the adult group (see **Figure 1**).

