# 6.6 Dose limiting toxicity (DLT)

During the time of enrollment into a given cohort, if any of the following events occur and are assessed to be vaccine related, further vaccination in that cohort will be suspended:

- Anaphylaxis reaction considered related;
- Generalized urticaria considered related;
- 1/3 trial subjects in that cohort with any severe unsolicited local reaction, if considered related and not manageable with simple measures (e.g. cooling, analgesia, nonsteroidal anti-inflammatory drugs [NSAID];
- Any possibly related AEs within 7 days of vaccination assessed to be potentially life-threatening (Grade 4);
- Any systemic SAE within 7 days of vaccination considered related;
- Any fever >40.0°C (>104.0°F) within 7 days of vaccination considered related;
- Occurrence of grade ≥3 adverse events that lasted at least 48 h and associated with vaccination, and for which there is no alternative feasible explanation, in more than 20% of participants (except local reactions: pain/tenderness, erythema/redness, and induration/swelling) after primary or booster inoculation;
- Occurrence of grade ≥3 clinical laboratory abnormality related adverse events with clinical manifestations, that not recovered for at least 8 days and associated with vaccination, and for which there is no alternative feasible explanation, in more than 20% of participants after primary or booster inoculation.

Approval from the SRC will be required prior to any further vaccination in the affected cohort. The SRC may call for the opening of a lower dose level cohort.

The same events will prompt IMP discontinuation for individual subjects as described in Section 6.9 until SRC review is completed.

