# 6.8 Criteria for early study termination of a subject

Under some circumstances, a subject's trial participation may be terminated early. This means that no further trial procedures (including data collection) will be performed on that subject beyond the specific date of early termination. The primary reason for early termination of the subject from the trial should be recorded in the electronic Case Report Form (eCRF "end of study visit" page) using the following categories. For screen failure subjects, refer to Section 9.1.11.

- 1. Safety stopping criteria: The SRC will review and evaluate the collected safety data periodically during the trial. A decision to stop treatment for an individual subject or to terminate the trial may be taken if safety concerns are identified by the SRC. Suspected unexpected serious adverse reactions (SUSARs) will immediately be reviewed by the SRC. They will trigger a temporary stop of IMP administration to new subjects in the respective dose level cohort for that vaccine until the SRC recommendation to continue or to permanently stop IMP administration of new subjects in the respective dose level cohort for that vaccine.
- 2. Adverse events: the subject has experienced an AE (irrespective of being related to the trial vaccine or trial-related procedures) that requires early termination because continued participation imposes an unacceptable risk to the subject's health and / or the subject is unwilling to continue participation because of the AE. If the subject is unwilling to continue because of the AE the primary reason for early termination in this case will be 'withdrawal due to AE' and not 'withdrawal of consent', see below. Any ongoing AEs leading to early termination will be followed by the investigator until resolution or stabilization.
- 3. Lost to follow up: the subject did not return to the study site and several attempts to contact the subject were unsuccessful. Attempts to contact the subject must be documented.
- 4. Withdrawal of consent: the subject wishes to withdraw from the trial. The primary reason for early termination will be 'withdrawal of consent' if the subject withdraws from participation due to a non-medical reason (ie, reason other than AE). The reason for withdrawal, if provided, should be recorded in the eCRF.

Note: all attempts should be made to determine the underlying reason for the withdrawal and, where possible, the primary underlying reasons should be recorded.

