# 11.0 Monitoring Committee

# 11.1 Safety Review Committee (SRC)

Safety Review Committee (SRC) will be established comprising investigators, Fosun medical representatives, and medical monitor, etc.

Key roles of the SRC are as follows:

- Before progression to the next age group (elderly group), assess the safety and tolerability data of the subjects in the adult group completed safety visits up to 14 days after prime vaccination, and decide whether to approve initiation of the dose cohort of elderly group. Data collected include vital signs, TEAEs, local reactions, blood/clinical laboratory data, and brief physical examination outcome.
- Before each dose cohort begins boost vaccination, for each dose cohort, assess the safety and tolerability data of the prime vaccination of subjects (including data collected at least up to 14 days post-vaccination) and, decide whether to approve initiation of boost vaccination of this dose cohort. Data collected include vital signs, TEAEs, local reactions, blood/clinical laboratory data, and brief physical examination outcome.
- Throughout the trial, assess whether to replace trial subjects permanently discontinued due to safety issues.
- Throughout the trial, the SRC may specific additional dose levels to be tested and an appropriate regime for enrollment and safety oversight.

See SRC charter for more information. The SRC will act according to written procedures described in SRC charter.

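### The SUSAR stop in Protocol 6.8 reaches only new subjects, so in one narrow case after boost approval a SUSAR brings immediate review but no automatic hold on the remaining boosts

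*Protocol*

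**What the plan says.** Protocol 6.8 (Criteria for early study termination of a subject) sets the SUSAR rule: "Suspected unexpected serious adverse reactions (SUSARs) will immediately be reviewed by the SRC". It continues: "They will trigger a temporary stop of IMP administration to new subjects in the respective dose level cohort". The stop lasts until the SRC recommends continuing or stopping permanently, and that recommendation is again worded for new subjects only. The term is not defined.

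Protocol 6.6 (Dose limiting toxicity) uses a wider remedy. On a trigger, "further vaccination in that cohort will be suspended", and SRC approval is needed to resume. It opens with "During the time of enrollment into a given cohort, if any of the following events occur". Its single-case triggers include "Any systemic SAE within 7 days of vaccination considered related". Related Grade 4 events and related fever above 40.0°C carry the same 7-day limit. Related anaphylaxis and related generalized urticaria have no time limit. The other three triggers are proportions: one third of the cohort for severe unsolicited local reactions, and two that require events "in more than 20% of participants after primary or booster inoculation" or equivalent wording. SAP 4.1.3 repeats this list and adds no SUSAR rule.

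Under Protocol 11.1 the SRC reviews at least 14 days of post-prime data for each dose cohort to "decide whether to approve initiation of boost vaccination of this dose cohort". Protocol 6.2 says that if the SRC finds subjects "safe with good tolerance after 14 days of observation, the boost vaccination will be conducted on Day 22". Table 2 allows ±2 days for that visit.

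**The concern.** A SUSAR stop exists to prevent further exposure until someone has judged the event. In a two-dose trial, a primed subject waiting for the boost is still to be exposed. In ordinary reading that person is not a new subject, and 6.6 shows that the protocol has wording that reaches boosts when it wants to.

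Once a cohort is fully primed, boosts are essentially the only injections left in it. A SUSAR rule that reaches only new subjects then holds nothing. Whether a boost due that day is given depends on how fast a committee or individual acts, not on a rule the site can follow.

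**Working it through.** The plan states no figure on this point, so the check is a comparison of the stopping rules with the visit calendar, followed by simple bounds.

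**Inputs.** Prime on Day 1; 14-day visit on Day 15 (±1); boost on Day 22 (±2) (Table 2). 24 subjects per cohort and 72 per age group (6.1). SRC boost gate needs 14-day data on all subjects in the cohort (Trial Summary, Trial Design; 11.1).

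**Step 1, calendar.**
- 7-day triggers in 6.6 end on Day 1 + 7 = Day 8.
- 14-day data are complete at Day 1 + 14 = Day 15.
- Boost falls on Day 22 − 2 = 20 to Day 22 + 2 = 24, which is 19 to 23 days after prime.

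After boost approval, anyone not yet boosted is therefore about 14 or more days past prime, and everyone in the cohort is primed. Apart from any replacements the SRC may allow under 11.1, no new subject remains in it.

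**Step 2, each provision against one SUSAR in an unboosted subject after approval.**

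| Provision | Holds the other boosts automatically? |
|---|---|
| 6.8 SUSAR stop | No; reaches new subjects only |
| 6.6 related systemic SAE, Grade 4, fever >40.0°C | No; 7-day limit passed |
| 6.6 more than 20% rules | No; 4/24 = 16.7%, 5/24 = 20.8%, so 5 cases are needed |
| 6.6 one-third rule | No; 24/3 = 8 cases are needed |
| 6.6 related anaphylaxis or generalized urticaria | Yes, if 6.6 is still in force (Step 3) |
| 6.7, 6.9 | No; act on the affected subject only |
| 6.8 (SRC may stop an individual or the trial), 4.3.1 (ad hoc SRC review), 6.10, 11.2, 14.3 | No; discretionary |

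**Step 3, is 6.6 still in force during boosting?** Its opening words tie it to enrollment. But boosting cannot begin until the whole cohort has 14-day data. If 6.6 ended with enrollment, its two references to booster inoculation could never operate. The only reading that gives them effect is that 6.6 runs through boosting. Section 11.2 likewise has the IDMC apply the DLT criteria on an ongoing basis. The anaphylaxis and urticaria triggers therefore still suspend boosts.

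**Step 4, exposure.** Upper bound per cohort: 24 − 1 = 23 other boosts. Lower bound: 0, if the others are already boosted or none falls due before the SRC decides.

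A point estimate is not available, because the documents give neither a priming pace nor a review duration. For illustration, assume priming evenly over calendar days 1 to 10, or 24/10 = 2.4 per day. The last subject reaches Day 15 on calendar day 10 + 14 = 24. Subjects primed on days 1 to 3 reach Day 22 on calendar days 22 to 24, so with no SRC review time about 3 × 2.4 = 7.2 boosts fall on day 24. Then 2.4 per day follow to day 10 + 21 = 31. A constant 2.4 per day over 10 days would need every subject boosted on Day 24, the last permitted day. Different assumptions move the count anywhere between the bounds.

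**The case against.** The strongest reply is that the gap is small and well surrounded. It needs a SUSAR beginning two weeks or more after prime, after approval, in an unboosted subject, while others still wait. A related systemic SAE within a week of an early boost is caught by 6.6 and suspends the cohort. SAEs reach Fosun within 24 hours of the investigator learning of them (10.2.3). The SRC must review at once, and investigators sit on it. The IDMC is required to look at unblinded data after an event that could suspend the study, and may expressly ask for boosting to be suspended (11.2). The investigator may seek ad hoc SRC review before further doses (4.3.1), and the amendment rules do not bar immediate protective action (14.3). The SRC and IDMC charters may contain the hold.

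All of that stands, and it keeps the point minor. It does not close the gap. Each of these is review or discretion, and 11.2 states that the study goes on as the protocol specifies unless the IDMC recommends otherwise. The default during review is to keep boosting.

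Three stronger readings are tempting, and the documents do not support them:
- A reader might infer that such a SUSAR goes unreviewed or that nobody can stop the boosts. The provisions above say otherwise.
- A reader might infer from its opening words that 6.6 lapses at the end of enrollment, so that even anaphylaxis would bring no hold. That would leave its booster criteria without effect.
- A reader might attach an expected number of boosts to the review period. The inputs for that are not in the documents.

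**Conclusion.** The point holds in a limited form. As written, 6.8 provides no automatic hold on pending boosts when a SUSAR other than related anaphylaxis or generalized urticaria begins about 14 or more days after prime in a not-yet-boosted subject of a cohort already approved for boosting. Review is immediate; the missing piece is a hold while it runs. The exposure is 0 to 23 other boosts per cohort of 24 and cannot be narrowed.

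This rests on three assumptions: new subjects means people not yet given IMP, 6.6 runs through boosting, and the unseen charters do not already supply a hold. It is a minor safety-rule correction.

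**What to change.** In Protocol 6.8, at both places, replace the reference to new subjects with all further IMP administration, prime and boost, until the SRC decides. State that this overrides any boost approval already given under 11.1.

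Apply the hold to all pending doses in the affected age group. The SRC and investigators are blinded and the three arms run in parallel. If an unblinded party narrowed the hold to one dose cohort and the other arms went on boosting, staff and subjects would see who shares the affected subject's arm. Solicited reactions recorded on diary cards for 14 days after each dose are primary endpoints, so that loss of blinding matters.

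State in 6.8 that boosts delayed by this hold may be given outside the ±2-day window, because the 6.7 allowance covers only a subject's own reasons for delay. In 6.6, replace the enrollment wording with a period that runs to the cohort's last boost. Align the SRC charter.

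The cost is a few sentences and no added data. The downside is some late boosts: up to 72 − 1 = 71 other subjects could be held, of whom 71 − 23 = 48 are outside the affected dose cohort.

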# 6.9 Criteria for premature discontinuation of trial vaccine application

Early (premature) study termination of a subject will by default prevent the subject from continued Trial Vaccine administration, as the subject will no longer be participating in the study.

In addition to early termination (see Section 6.8) criteria, other situations may apply in which subjects may continue participating in the trial (eg, contributing safety data according to protocol) but Trial Vaccine application is discontinued selectively. Regardless of the reasons for discontinuation of Trial Vaccine application, this must be documented as protocol deviation. Even if the subject is deemed ineligible to continue to receive Trial Vaccine, all efforts should be made to continue the collection of safety data according to protocol. In addition, the one primary reason for early discontinuation of Trial Vaccine application should be recorded in the eCRF, "end of Trial Vaccine application" page using the following categories.

- 1. Adverse events: the subject has experienced an AE (irrespective of being related to the Trial Vaccine or trial-related procedures) for which subsequent Trial Vaccine applications impose an unacceptable risk to the subject's health, but the subject will continue trial participation or other study procedures for safety.
- 2. Lost to follow up: the subject did not return to the clinical and several attempts to contact the subject were unsuccessful. Attempts to contact the subject must be documented
- 3. Withdrawal of consent: the subject wishes to withdraw from the trial. The primary reason for early termination will be 'withdrawal of consent' if the subject withdraws from participation due to a non-medical reason (ie, reason other than AE). The reason for withdrawal, if provided, should be recorded in the eCRF.
- 4. Premature study termination by Fosun, a regulatory agency, the IEC/IRB, or any other authority. If the clinical study is early terminated by the Fosun, the investigator is to promptly inform the study subjects and local EC/IRB and should assure appropriate follow up for the subjects. The primary reason for early termination in this case will be 'trial termination'.
- 5. Subject's death during trial participation.
- 6. Protocol Deviation: a protocol deviation is any change, divergence, or departure from the study design or procedures of a study protocol. The subject may remain in the trial unless continuation in the trial jeopardizes the subject's health, safety, or rights (see Section 7.4).
- 7. Pregnancy: any subject who, despite the requirement for adequate contraception, becomes pregnant during the trial will not receive further Trial Vaccine applications. Pregnant subjects should, however, be asked to continue participating in the trial contributing data to the safety follow-up according to protocol. In addition, the site should maintain contact with the pregnant subject and complete a "Clinical Trial Pregnancy Form" as soon as possible. The subject should be followed-up until the birth of the child, or spontaneous or voluntary termination; when pregnancy outcome information becomes available, the information should be captured using

the same form. Data obtained from the "Clinical Trial Pregnancy Form" will be captured in the safety database.

# 8. Other.

Note: the specific reasons should be recorded in the "specify" field of the eCRF.

# 6.10. Premature termination or suspension of the trial

# 6.10.1 Criteria for premature termination or suspension of the trial

The trial will be completed as planned unless one or more of the following criteria are satisfied that require temporary suspension or early termination of the trial.

- New information or other evaluation regarding the safety or efficacy of the investigational vaccine that indicates a change in the known risk/benefit profile, such that the risk/benefit is no longer acceptable for subjects participating in the trial.
- SRC/IDMC recommends that the trial should be suspended or terminated.
- It deviates from Good Clinical Practice (GCP) significantly, so that the primary objective of the trial cannot be achieved or the safety of subjects may be compromised.

# 6.10.2 Procedures for premature termination or suspension of the trial

If the Fosun, an institutional review board (IRB)/independent ethics committee (IEC) or regulatory authority elects to terminate or suspend the trial or the participation of an investigational site, a trial-specific procedure for early termination or suspension will be provided by the Fosun.

## 7.0 Inclusion and exclusion criteria

All entry criteria, including test results, need to be confirmed prior to randomization.

#### 7.1 Inclusion and exclusion criteria for adults

#### **Inclusion criteria:**

- 1. Male or female subjects of  $\geq$ 18 years old and  $\leq$ 55 years old with body mass index (BMI)  $\geq$ 18 and  $\leq$ 30 at the Screening Visit.
- 2. Individuals who are in good health condition at the time of entry into the trial as determined by medical history, physical examination (including vital signs, ECG) and eligibility screening test (hematology, blood chemistry and urine analysis) and clinical judgment of the investigator at Screening Visit.
- 3. The subject can provide with imformed consent and signs and dates a written informed consent form (ICF) prior to the initiation of any trial procedures.
- 4. They must be able to understand and follow trial-related instructions.
- 5. They must be willing and able to comply with planned visits, treatment schedule, laboratory tests and other requirements of the trial.
- 6. Negative in antibodies screening of SARS-CoV-2 (fingerstick).
- 7. Normal in chest CT scans (no imaging features of COVID-19).
- 8. Axillary temperature≤37.0°C.
- 9. Negative SARS-CoV-2 test in throat swabs by RT-PCR.
- 10. Women of childbearing potential (WOCBP) must have a negative serum β-hCG at Screening Visit. Women that are postmenopausal (Menopause ≥12 consecutive months) or permanently sterilized will be considered as not having reproductive potential.
- 11. WOCBP must have used effective contraception 14 days prior to screening and agree to use effective contraception continuously during the trial period, from 14 days prior to Screening Visit to 60 days after the last immunization.
- 12. WOCBP must agree not to donate eggs (ova, oocytes) for the purposes of assisted reproduction during trial, starting from Screening Visit and continuously until 60 days after be given the last immunization.
- 13. Men who are sexually active with a WOCBP and have not had a vasectomy must agree to practice a effective form of contraception with their female partner of childbearing potential during the trial, starting from Screening Visit and continuously until 60 days after be given the last immunization.
- 14. Men must be willing to refrain from sperm donation, starting from Screening Visit and continuously until 60 days after receiving the last immunization.

#### **Exclusion criteria:**

- 1. Have had any acute illness, as determined by the investigator, with or without fever, within 72 h prior to the prime vaccination. An acute illness which is nearly resolved with only minor residual symptoms remaining is allowable if, in the opinion of the investigator, the residual symptoms will not compromise their well-being if they participate as trial subjects in the trial, or that could prevent, limit, or confound the protocol-specified assessments.
- 2. Are breastfeeding on the day of Screening Visit or who plan to breastfeed during the trial, starting from Screening Visit and continuously until at least 90 days after the last immunization. Women or partners who plan to become pregnant within 1 year post the screening visit.
- 3. Have a known allergy, hypersensitivity, or intolerance to the planned vaccine for trial including any excipients.
- 4. Used to have a history of hypersensitivity or serious reactions to vaccinations.
- 5. Received any vaccination within 4 weeks prior to Visit 1.
- 6. Don't agree to not be vaccinated during the trial, starting from Screening Visit and continuously until 28 days after receiving the last immunization, except emergency vaccination (e.g. rabies vaccine, tetanus vaccine).
- 7. Had any medical condition (e.g., autoimmune disease) or any major surgery (e.g., requiring general anesthesia) within the past 5 years, which in the opinion of the investigator, could compromise their well-being if they participate as trial subjects in the trial, or that could prevent, limit, or confound the protocol-specified assessments.
- 8. Have any surgery planned during the trial, starting from Screening Visit and continuously until at least 90 days after the last immunization.
- 9. Had any chronic use (more than 14 continuous days) of any systemic medications, including immunosuppressant or other immune-modifying drugs, within 6 months prior to Screening Visit unless in the opinion of the investigator, the medication would not prevent, limit, or confound the protocol-specified assessments or could compromise safety of subjects.
- 10. Had administration of any immunoglobulins and/or any blood products within the 3 months prior to Screening Visit.
- 11. Had administration of another investigational product including vaccines within 60 days or 5 half-lives (whichever is longer), prior to Screening Visit.
- 12. With known history of AIDS or HIV test positive.
- 13. Have active HBV or HCV infection, through medical inquiry.
- 14. History of SARS, SARS-CoV-2 or MERS infection. Suspected SARS patients should be screened for SARS antibodies.
- 15. Previously participated in a clinical trial involving lipid nanoparticles.
- 16. Are subject to exclusion periods of other clinical trials or simultaneous participation in another clinical trial.
- 17. Have any affiliation with the study site (e.g., are close relative of the investigator or dependent person, such as an employee or student of the study site).

- 18. Have a history of drug abuse or known medical, psychological or social conditions within the past 5 years. In the opinion of the investigator, could comprise their well-being if they participate as trial subjects in the trial, or that could prevent, limit, or confound the protocol-specified assessments.
- 19. Have a history of narcolepsy.
- 20. Have history of alcohol abuse or drug addiction within 1 year prior to Screening Visit.
- 21. Have a history of or suspected immunosuppressive condition, acquired or congenital, as determined by medical history and/or physical examination at Screening Visit.
- 22. Have any abnormality or permanent body art (e.g., tattoo), in the opinion of the investigator, would obstruct the ability to observe local reactions at the vaccination site.
- 23. Have had any blood loss >400 mL, e.g., due to donation of blood or blood products or injury, within the 28 days prior to Screening Visit or plan to donate blood or plasma during the trial, starting from Screening Visit and continuously until at least 28 days after be given the last immunization.
- 24. Travel or live in any country or region with a high SARS-CoV-2 infection risk (as defined at Screening Visit) within the 14 days prior to Screening Visit.
- 25. They plan to visit any country or region with a high SARS-CoV-2 infection risk (as defined at Screening Visit), from Screening Visit until 14 days after be given the last immunization.
- 26. Symptoms of COVID-19, e.g., respiratory symptoms, fever, cough, shortness of breath and breathing difficulties.
- 27. Have had contact with confirmed COVID-19 patients or persons tested positive for SARS-CoV-2 within the 30 days prior to Screening Visit.
- 28. Are vulnerable persons, e.g., soldiers, subjects in detention, CRO or Fosun staffs or their family members.

